### **7.2. Separation of Whole Blood Specimen and Shipment**

This step will be done in the field laboratory. During enrolment, blood collected in the microtainer will be separated for quantitative G6PD screening test by Standard G6PD (SD Biosensor, ROK), Hb measurement by HemoCue and Sahli, serological test, and qPCR.

Ten microliters will be used for Standard G6PD (SD Biosensor), 30 µL for hemoglobin measurement (10 µL for HemoCue and 20 µL for Sahli). The remaining

blood will be centrifuged at 5000 RPM for 10 minutes at room temperature. Plasma (supernatant, yellow transparent top layer) will be transferred into new screwed cryogenic tubes. Tubes containing plasma for serological test and pellet for qPCR will be immediately stored in the -20°C freezer. Every 2 days, tubes containing plasma will be shipped to Jakarta for serological assay using cold-chain, and monitored for temperature during transportation. During follow up, blood will be separated into plasma (for serological analysis when needed) and pellet for qPCR to detect recurrence.

### **7.3. Blood smear Giemsa staining and microscopic reading**

Blood films will be dried in room temperature overnight, and fixed with methanol (thin smear only) before it is stained using 3% Giemsa made by mixing the stock solution with buffer. The stain will be gently poured into the slides until they are totally covered. After 45-60 minutes, slides will be rinsed with water and allowed to dry and read under binocular microscope with 1,000 magnification (20).

WHO certified microscopist will read the slides in the field, and cross check will be done at Jakarta. Asexual stages and gametocytes will be counted separately. For LMF, parasites will be counted against leucocytes in the thick smear. Density will be recorded as the number of parasites found per 200 leucocytes. A conversion to number of parasites in microliter of blood will be conducted under the assumption of one microliter of blood contains 8,000 leucocytes.

For LMS, parasites will be counted against RBC found in 20 HPF. Density will be recorded as number of parasites per 1 microliter. A conversion to number of parasites in microliter of blood will be conducted under the assumption of one microliter of blood contains 5,000,000 RBC.

## **7.4. Serological Test**

### **7.4.1. Gold-standard Luminex**

This test will measure IgG antibodies titres to a panel of 8 specially selected *P. vivax* antigens in plasma samples and will be performed using a Luminex MAGPIX® bead array system. This test will be run in plate format containing blank (in duplicate), positive (singlicate), and negative (singlicate) controls. Blank contains only PBT(1x PBS, 1% BSA, 0.05% Tween-20 (Sterile filter the PBS-BSA prior to

adding Tween-20). A 2-fold serial dilution from 1/50 to 1/25,600 of positive controls will be run in singlicate. A 1/100 dilution of plasma sample will be run in each well.

#### **7.4.2. Point-of-Care anti-*P. vivax* antibody detection test**

This test will be done on site by finger prick. This laminar flow rapid diagnostic test will measure IgG antibodies titres to a fragment of the *P. vivax* RBP2b (reticulocyte binding protein 2b) antigen in whole samples. This test will require placing 15µL of blood and a buffer into a laminar flow cartridge. The test can be read after 10-15 minutes either by eye or with a specific reader (if quantification is desired).

#### **7.5. Glucose-6-Phosphate Dehydrogenase (G-6-PDH) Screening Test**

Quantitative G6PD screening test will be performed to all schoolchildren. Standard G6PD (SD Biosensor, ROK) will detect amount of G6PD enzyme in U/gHb. The result is shown as number of U/gHb. G6PD normal is defined as G6PD level >4 U/g Hb for male or >6 U/gHb for female.

#### **7.6. Hemoglobin Level Measurement**

Hemoglobin level will be measured in the field lab using HemoCue® (HemoCue AB, Angelholm, Sweden) as golden standard. After mix properly, 10 µL blood will be transferred into the Hemocue microcuvette. Blood filled microcuvette will be inserted into the Hemocue Hb 301+ automated machine system (HemoCue AB, Angelholm, Sweden). The haemoglobin result will be then displayed after about 30 to 45 seconds in g/dL units. Result will be saved, and transferred to PC. Result will also be recorded in the Case Report Form manually. Additionally, Sahli's hemoglobinometer and Standard G6PD (SD Biosensor Inc., Deogyong-daero, Korea) will be evaluated.

For Sahli's method, 20 µL blood will be transferred by micropipette into the tube containing 2 g% of HCl. The solution is left for 10 minutes, then diluted with distilled water drop by drop until the colour changes to matched the comparator in the Sahli's hemoglobinometer.

#### **7.7. Gazelle® (Hemex Health, USA) test**

This point-of-care test will be done on site during enrolment. It will detect the presence of malaria paramagnetic byproduct hemozoin using magneto-optical detection (MOD) principle. A pipette is used to drop 10uL from skin vasculature or 15uL of whole blood from finger prick into the cartridge bottom, and mixed with 85uL of Gazelle Diluent (mostly water). The cartridge is then manually inserted into the chamber in the Reader. Inside the cartridge, blood sample is sonicated, causing it to lyse the blood and release hemozoin. The magnetic field is used to align the hemozoin. The alignment will block the transmission of light which is proportional to the quantity of hemozoin in the sample. The malaria positive/negative (qualitative) test result is displayed on the Reader within approximately one minute. The result will be stored in the Reader's memory which can be printed or transferred to a laptop or printer.

The machine will also identify hemoglobin type by electrophoresis on microchip. Twenty microliter of finger pricked blood sample will be inserted into the cartridge and read within 10 minutes.

#### **7.8. qPCR Malaria Speciation**

This step will be performed at Universities of Indonesia and Oxford Clinical Research Laboratory (UIOCRL), Jakarta. DNA will be extracted from 200 µL of red cell pellet using a commercially available kit. All blood samples will be screened for the presence of malaria parasites using Real-Time PCR targeting a genus-specific, conserved region of 18S rRNA. For all positive samples, speciation and quantification will be conducted using probe-based Real-Time PCR, which will amplify the multicopy gene 18S rRNA (21).

#### **7.9. Genotyping**

All samples from schoolchildren found to be qPCR-positive for *Plasmodium falciparum* or *Plasmodium vivax* will undergo genotyping using a targeted amplicon deep sequencing approach to genotype clones within individual infections, measure genetic relatedness, and discriminate new and existing infections. Each sample will undergo PCR-amplification of highly polymorphic genomic regions followed by next-generation sequencing (22,23).

#### **7.10. Storage of the Specimens**

Malaria stained blood smears will be stored in the UIOCRL, Jakarta. Blood samples will be stored in the -20°C freezer at UIOCRL, Jakarta until further process.

## **8. Data management and analysis**

### **8.1. Data management**

Qualitative and quantitative data will be collected during study period. Research team will visit selected elementary schools to conduct demographic census of study participants with the assistance of class teacher and cadres.

[figure not shown]
Body weight and temperature, history of fever, results of malaria examination and other substudies, anti-malarial treatment, AE, SAE (if any) will be recorded in Case Report Forms. CRF will only contain ID number of the subjects instead of their full name. Labelling of specimen will be given by adding activity number to the subject ID, e.g. QQxxx-0 (enrollment), QQxxx-1 (follow up 1), etc. (QQ=school initial, xxx=subject number)

After end of study, hard copy files will be stored for at least 5 years at UIOCRL. All CRFs will be transferred into electronic database. Only authorized individuals using secure, authorized computers may access this data management system.

### **8.2. Sample size consideration**

Sample size is calculated based on the difference in the incidence of *P. vivax* infection between the intervention and control arm. The impact of the SSAT intervention is expected to reduce incidence of *P. vivax* in schoolchildren compared to control group. Our study in 2013 found *Pv* prevalence of ~20% by PCR (2). Different effect and sample sizes were simulated using a specific mathematical transmission model (24) and statistical power calculated. With the proposed sample size of 350 children per arm, we will have a power of >90% to detect a significant difference (Figure 3). Assuming 15% exclusion rate, we will recruit 400 children per arm.

**Figure 3. Simulation of various sample size (n=50-500) to detect significant difference in the proportion of infected subjects during follow up period.**

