	
P. vivax.
 
SSAT intervention is expected to reduce incidence of P. vivax in comparison to standard care. With the previous prevalence rate of 20%, we will have a power of >90% to detect a significant difference with the sample size of 350 children per group. We will anticipate the exclusion of 15% by recruiting 400 children per group.

Lay Summary
	
This study evaluates an experimental serological diagnostic technique intended to identify people at high risk of having dormant malaria parasites in their liver. The findings will assess the ability of this sero test to identify those carriers.
 
800 children living in eastern Indonesia will be individually randomised to the experimental serologic test or routine care.
 
Children in the serological diagnosis arm will be screened for the presence of antibodies to a previously validated panel of malaria antigens optimized for sensitivity to infection during the prior 9 months. Furthermore, they also will be screened by microscopy. If positive by either test, they will be treated for that malaria infection.
 
Children assigned to routine care will be screened by microscopic examination and treated when they show or have history of symptoms in the last 3 days.
 
After initial screening and treating according to diagnostic technique, all children will be actively followed for 9 months with PCR detection every 4 weeks.
 
During 9 month follow up, all children becoming acutely ill and proven to be positive for malaria by microscopy will be treated, in addition, all asymptomatic children will be treated at the final time point.
 
POC serology test will be performed at baseline and final timepoint on all children in both arms. The results from this POC serology test will not be used to inform diagnosis or treatment in any way at either of the timepoints.
 
None of these blood samples will be collected by venopuncture but instead minimally invasive lancet devices will be used.

Sero-diagnostic test
	
Quantitative measurement of antibody titres to a panel of 8 specially selected P. vivax antigens in study subject plasma samples using a Luminex MAGPIX® bead array system. This testing will be done at the Eijkman Institute in Jakarta. The results will be generated in no

	more than 7 days.
--	-------------------

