### **6.2. Schools selection and demographic census**

Before the start of the study, a serological survey will be conducted to select the schools. Blood samples will be collected from 20 randomly selected children from each school in Weoe for serological screening with Luminex. Only schools with sero-prevalence of 30-70% will be eligible for enrollment. Maximal number of selected schools will be 6-7, where 800 children will be individually randomized. Demographic census will be conducted during which name, date of birth/age, gender, village, hamlet, parents/guardian will be recorded (census form). Photograph will be taken from each participants to ensure the correct identification for treatment administration and follow up.

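### Recruiting 400 per arm with 15% excluded leaves 340 children per arm, not the 350 for which more than 90% power is stated; the shortfall is minor

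*Protocol*

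**What the plan says.** Protocol section 8.2 (Sample size consideration) gives the power and the size it belongs to: "With the proposed sample size of 350 children per arm, we will have a power of >90% to detect a significant difference". The next step is the recruitment target: "Assuming 15% exclusion rate, we will recruit 400 children per arm".

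The Study Synopsis (section 3) makes the same two statements: "we will have a power of >90% to detect a significant difference with the sample size of 350 children per group", followed by "We will anticipate the exclusion of 15% by recruiting 400 children per group".

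Section 6.2 confirms the total: "Maximal number of selected schools will be 6-7, where 800 children will be individually randomized". The synopsis splits this as 400 per arm.

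On the basis of the power, section 8.2 says: "Different effect and sample sizes were simulated using a specific mathematical transmission model (24) and statistical power calculated". It cites a PCR prevalence of about 20% from 2013 and refers to Figure 3, whose caption covers sample sizes from 50 to 500. The text gives no numerical effect size. Nowhere does the protocol state how many children per arm should remain after exclusion.

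**The concern.** Three numbers are given, and any two of them fix the third: 400 recruited per arm, 15% excluded, 350 on which the power rests. As written they cannot all be true. If 15% of the 400 are excluded, the number left is below 350, so the quoted power belongs to a slightly larger sample than the plan delivers under its own assumption.

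The 15% does appear to come off the 400. The synopsis randomises 400 per arm. The exclusion criteria in section 6.4 (G6PD activity and haemoglobin) are measured on blood taken at enrolment under section 6.6, and the time frame in Appendix C puts randomisation in the month before enrolment starts.

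At stake is whether the stated power describes the planned trial. No endpoint, analysis method or study procedure depends on it.

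**Working it through.** **Inputs.** Size for the stated power: 350 per arm (section 8.2, synopsis). Exclusion: 15% (same places). Recruitment: 400 per arm, 800 in total (section 8.2, synopsis, section 6.2).

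**1. Reproducing the stated 400.** Adding 15% to 350 gives 350 × 1.15 = 402.5, which rounds down to 400. This is probably how the figure arose, though the protocol does not say so.

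**2. The inflation that retains 350.** N / (1 − d) = 350 / 0.85 = 411.8, so 412 per arm and 824 in total. Check: 412 × 0.85 = 350.2.

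**3. What 400 leaves.** 400 × (1 − 0.15) = 340 per arm. Shortfall: 350 − 340 = 10 per arm; 10 / 350 = 2.9%. Conversely, 400 leaves 350 only if 50 / 400 = 12.5% are excluded.

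**4. Sensitivity of power to 340 in place of 350.** The simulated power cannot be reproduced from the text, so this step only gauges relative size. Assumptions: two-sided 5% test and the normal approximation, in which the standardised effect scales with √n.

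- If power were exactly 90% at 350, the standardised effect is 1.960 + 1.2815 = 3.2415. At 340 it is 3.2415 × √(340/350) = 3.195, and 3.195 − 1.960 = 1.235, which is a power of about 89.2%. The loss is about 0.8 points. Solving for the effect with control proportions of 20%, 30%, 40% and 50% gives the same result each time.
- To have 90% at 340, the effect at 350 must be 3.2415 / √(340/350) = 3.289, and 3.289 − 1.960 = 1.329, which is a power of about 90.8%.

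**5. The same comparison with an assumed 20% control proportion.** The 20% is borrowed from the 2013 prevalence and is not a nine-month incidence. The formula is power = Φ{[√n·|p₁ − p₂| − 1.96·√(2p̄(1 − p̄))] / √[p₁(1 − p₁) + p₂(1 − p₂)]}, where p̄ is the mean of p₁ and p₂.

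| Assumed reduction | Power at 350 | Power at 340 | Loss (points) |
|---|---|---|---|
| 40% | 82.4% | 81.3% | 1.1 |
| 45% | 91.0% | 90.2% | 0.8 |
| 50% | 96.1% | 95.6% | 0.5 |

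In the rows where power at 350 exceeds 90%, as the protocol states, the loss is 0.8 points or less.

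**The case against.** The strongest reply is that this is rounding. A recruitment target of 400 is a round number, 340 is within 3% of 350, and power moves by about a point. That is fair on size, and it is why the point is minor. It does not make the three figures agree.

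The second reply is that the power claim may still be true. This stands. The protocol says more than 90%, not 90%, and on the approximation above power at 340 remains over 90% if it was at least about 90.8% at 350. The simulated range of 50 to 500 includes 340, so the authors can read the answer off directly. The approximation is also not the trial's own calculation: power came from a transmission model, and section 8.3 compares clone incidence rates over person-time.

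Two stronger readings are tempting and are not supported:

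- **That the trial is underpowered.** A reader might infer this from the 89.2%. That figure depends on power being exactly 90% at 350, the floor that the protocol's wording excludes. Without an effect size or Figure 3, no breach of 90% is shown.
- **That the 15% leaves nothing for loss over nine months, so that the real size is well under 340.** The protocol does not define what the 15% covers and gives no separate loss rate. Section 6.7 keeps all children in follow-up to month 9 even if visits are missed, and section 8.3 uses person-time, so a child with partial follow-up still contributes.

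**Conclusion.** The inconsistency is real and appears in both section 8.2 and the synopsis: 400 less 15% is 340, not 350. It is a minor slip, most simply explained by multiplying by 1.15 when dividing by 0.85 was needed. The shortfall is 10 children per arm (2.9%), and the effect on power is about one percentage point or less.

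The subtraction rests only on the protocol's own figures. The power effect rests on a two-sided 5% test and a normal approximation, and shows relative sensitivity only. Whether power at 340 is above or below 90% cannot be settled from the available text.

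**What to change.** In section 8.2 and in the sample size paragraph of the synopsis, state that 400 recruited per arm with 15% exclusion leaves 340 per arm, and report the power from the existing simulation at n = 340 in place of n = 350. No new simulation design and no change to recruitment or procedures is needed.

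The cost is one sentence in each of two places and a slightly less favourable stated power. Recruiting 412 per arm would also restore consistency, but it means 24 more children for about a point of power. Rewriting the exclusion rate as 12.5% is not recommended: it would fit the assumption to the recruitment number, and nothing in the protocol supports that rate.

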### 8.3. Data analysis

*Plasmodium vivax* incidence is defined as the total number of new genetically distinct *P. vivax* clones per child per detected during the follow up period. The analysis will use the comparison of two incidence rates between SSAT group and control group. For comparison, data will be entered as the number of recurrent *Pv* (numerators) and the total length of time people contributed in the cohort (person-time) as denominators. We will calculate the exact probabilities (Fisher's and Mid-P), the rate ratio with the exact confidence intervals and the measures of the impact of intervention. We will report the 95% of confidence interval for this comparison. Measures of the impact of intervention are computed for the prevented fractions in the exposed and in the population and the preventable fraction in the population.

As secondary endpoints, we will use Kaplan-Meier method to detect differences in the time-to-first recurrence of *Pv* by PCR in SSAT and control arms. The log-rank test is used to detect any difference between the two groups. Cox proportion hazard will be used to measure the effect size.

Multiple recurrences of *P. vivax* infections will be calculated during follow up. Number of events will be calculated, divided by the total length of time people

contributed in the cohort (person-time) as denominators. We will calculate the exact probabilities, rate ratio with the exact confidence intervals, and the measures of the impact of intervention using same tests as above.

Symptomatic recurrent *P. vivax* is defined as LMF positive with fever ( $\geq 37.5^{\circ}\text{C}$ ) or history of fever in the last 3 days during follow up. The same statistical test will be performed to compare both groups.

Difference of seropositivity between the two arms before and after the intervention will be calculated using chi-square test with p value  $< 0.05$  as limit of significance.

Sensitivity, specificity, positive predictive value, and negative predictive value of POC *Pv* antibody rapid test will be reported with Luminex as the golden standard.

Type and number of AE and SAE will recorded, and reported with total length of time people contributed in the cohort (person-time) as denominators.

*Plasmodium* gametocytes prevalence in LMF and LMS will be calculated as the number positive for gametocytes by each diagnostic method divided by the number of subject examined. Diagnostic performance will be derived using  $2 \times 2$  contingency to determine sensitivity, specificity, positive predictive value (PPV), negative predictive value (NPV). Results of qPCR detection will be used as the gold standard for diagnostic method evaluation. All statistics will be reported as absolute values with their 95% confidence interval (95% CI). To assess the significance of different results of LMF and LMS methods, we will apply McNemar's chi-square test on  $2 \times 2$  contingency tables derived from the results of each detection method.

We will evaluate durability analysis by measuring population half-life of the existence of *Plasmodium* gametocyte detected by LMS samples. Gametocyte prevalence-based approach will use data on the appearance and disappearance of any circulating gametocytes according to the prevalence at month 0 and the prevalence at the time when they are fully cleared from skin vasculature.

Sensitivity, specificity, positive predictive value, and negative predictive value of hemozoin detection will be reported using microscopic Giemsa examination as golden standard.

Hemoglobin measurement using Sahli method and Standard G6PD will be compared to HemoCue by t test.

Hemoglobinopathy rate will be reported as descriptive value.

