## **5. Objectives and Endpoints**

**5.1. Primary objective:** to determine the efficacy of a Serological Screening and Treatment (SSAT) intervention for the prevention of recurrent *P. vivax* malaria.

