### 6.3. Study design and study overview

The study design is a randomized controlled trial with serological screening and treatment as the intervention. Selected schoolchildren will be allocated into two study arms: (1) serological screening and treatment (SSAT), and (2) routine care as control arm.

At enrolment, in the SSAT arm, individuals found *P. vivax* positive by either serological (Luminex) or Giemsa stained microscopic examination regardless of the symptoms will receive supervised treatment (direct observation) with high dose PQ (daily 1 mg/kg BW) for 7 days ( $P_o=P_v$ ). In the control arm, only symptomatic individuals found *P. vivax* positive by Giemsa stained microscopic examination will receive the same regimen ( $P_o=P_v$ ). In addition, in the treated children of both arms, dihydroartemisinin-piperaquine (DHA-PP) will be given as blood schizontocide according to body weight. All other species (*P. falciparum*, *P. malariae*) found by Giemsa stained microscopic examination will be treated according to national guideline. Serological examination will be performed by Luminex (done at Eijkman, Jakarta) and point-of-care (POC) antibody detection using rapid test on site

Follow up will be performed monthly for 9 months. During this period, 400  $\mu$ L of finger pricked blood samples will be collected from all children in both arms. These samples will be tested for malaria presence by PCR which will be done at EO CRU, Jakarta. However, children with clinical symptoms (body temperature of  $\geq 37.5^\circ\text{C}$  and/or history of fever within 3 days), will be examined by Giemsa stained microscopy on site, and treated if positive (any species) according to national guideline (unsupervised).

At the last follow up, a mass blood survey will be conducted to both arms for *Pv* serological test, LMF, and PCR. Those found positive by LMF for any species will be treated regardless of their symptoms.

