## 6.6. Enrolment

During enrolment, finger pricked blood samples will be collected from all participants. At this activity, body temperature will be recorded using infrared thermometers, body weight will be scaled, history of fever within 3 days and taking antimalarial drugs within last 2 weeks will be recorded. Finger pricked blood samples will be made into malaria blood smear and tested by POC Pv antibody rapid detection. A total of 400  $\mu$ L will be collected into microtainer tube containing EDTA to be sent to field laboratory, and separated for various tests, e.g. serology (Luminex), PCR, Hb, G6PD, and Hemex.

All participants' blood samples will be tested for the presence of antibodies to a validated panel of *P. vivax* antigens (using a gold-standard laboratory test) at the Eijkman Institute for Molecular Biology, Jakarta. Blood samples will be shipped every 2 days, and the result will be reported to the field team within no more than 1 week.

On site, blood slides will be Giemsa stained (see 7.3) and assessed by microscopy with 1000x magnification. Screening for G6PD deficiency will be performed quantitatively by Standard G6PD (SD Biosensor, ROK) with the cut off of 4 U/g Hb (male) or 6 U/g Hb (female) on the same day of blood collection. Hb level will be measured using HemoCue and Hb Sahli. Other substudies (LMS, hemozoin detection, hemoglobinopathy) will also be conducted (see 6.10)

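### No planned efficacy analysis uses baseline serostatus, so the trial cannot separate benefit in test-positive children from dilution by seronegatives

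*Protocol*

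**What the plan says.** The primary objective (Protocol, section 5.1) is "to determine the efficacy of a Serological Screening and Treatment (SSAT) intervention for the prevention of recurrent" *P. vivax* malaria. For the primary result, section 8.3 states: "The analysis will use the comparison of two incidence rates between SSAT group and control group". It names exact tests and a rate ratio on events per person-time. The secondary efficacy analyses (time to first recurrence by Kaplan-Meier, log-rank and Cox; multiple recurrences; symptomatic recurrence) are also described as whole arm against whole arm, with no covariate, stratum or subset.

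Serology is available for everyone at baseline. Section 6.6 says that all participants' "blood samples will be tested for the presence of antibodies to a validated panel of" *P. vivax* antigens. In section 8.3 serostatus appears only as a before-and-after outcome and as the reference for the point-of-care test.

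Treatment at enrolment differs by arm (section 6.3). In the SSAT arm, children found "positive by either serological (Luminex) or Giemsa stained microscopic examination regardless of the symptoms will receive supervised treatment". In the control arm, only symptomatic children found "positive by Giemsa stained microscopic examination will receive the same regimen".

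Section 6.2 sets the expected serological mix: "Only schools with sero-prevalence of 30-70% will be eligible for enrollment". Section 8.2 gives the power: "With the proposed sample size of 350 children per arm, we will have a power of >90% to detect a significant difference (Figure 3"). It cites an earlier "prevalence of ~20% by PCR (2") without stating an effect size in the text.

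**The concern.** Three groups of children enter the whole-arm ratio:

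- **Seropositive children.** A positive serology leads to treatment in SSAT and to nothing in control.
- **Seronegative, slide-negative children.** They are managed alike in both arms.
- **Asymptomatic slide-positive children.** They are treated at enrolment only in SSAT, whatever their serology.

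A single ratio blends all three. If it came out near 1, the plan could not say whether treating test-positive children failed, whether the test missed the children who recur, or whether a real benefit was averaged over many children whose care did not change. If it came out clearly below 1, part of the effect could belong to microscopy screening and not to serology.

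This matters for a proof-of-concept trial. The Synopsis describes the product as a test for finding hypnozoite carriers, and its lay summary says the findings will assess how well the test does so. No analysis in section 8.3 relates baseline serostatus to recurrence or to the treatment effect.

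**Working it through.** **1. The plan's own figure.** The power above 90% cannot be reproduced, because the text gives no effect size and Figure 3 is not shown. As a guide, take 350 per arm, a control proportion of 20% (the cited prevalence used as a 9-month proportion, an assumption) and a two-sided 5% test of two proportions:

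power = Φ{ [ |p1 − p2| − 1.96·√(2p̄(1 − p̄)/n) ] / √([p1(1 − p1) + p2(1 − p2)]/n) }, where p̄ is the mean of p1 and p2.

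An overall reduction of 30% gives 56%, 40% gives 82% and 50% gives 96%. Power of 90% needs a reduction of about 44% (20% to 11.1%).

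**2. Dilution.** Let s be the share seropositive. Assume a 9-month risk of 30% in seropositives and 10% in seronegatives, with treatment halving risk in seropositives and doing nothing in seronegatives. Then control risk = 0.30s + 0.10(1 − s) and SSAT risk = 0.15s + 0.10(1 − s).

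- s = 0.3: 0.160 against 0.115, ratio 0.72
- s = 0.5: 0.200 against 0.125, ratio 0.63
- s = 0.7: 0.240 against 0.135, ratio 0.56

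The ratio among seropositives is 0.50 throughout.

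**3. Power of each comparison.** Take n = 400 × 0.85 = 340 per arm, so 340s seropositives per arm.

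Worked case, s = 0.5:
- All children: p̄ = 0.1625, so (0.075 − 1.96 × 0.02829)/0.02815 = 0.69 and Φ = 0.76.
- Seropositives, 170 per arm: p̄ = 0.225, so (0.150 − 1.96 × 0.04529)/0.04456 = 1.37 and Φ = 0.92.

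| Seropositive | All, crude | All, stratified by serostatus | Seropositives only |
|---|---|---|---|
| 30% | 40% | 41% | 73% |
| 50% | 76% | 77% | 92% |
| 70% | 94% | 95% | 98% |

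The stratified column is a Mantel-Haenszel test simulated with 20,000 trials per row. The same simulation agrees with the other two columns to within about one point.

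**4. Other assumptions.** Fix the control proportion at 20%, use 350 per arm, keep the halving in seropositives only, and vary how strongly serostatus predicts infection (RR = risk in seropositives divided by risk in seronegatives). Entries are all crude / all stratified / seropositives only, in %.

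| Seropositive | RR 1 | RR 2 | RR 4 |
|---|---|---|---|
| 30% | 17/17/53 | 36/36/76 | 61/64/91 |
| 50% | 41/41/75 | 66/66/88 | 82/84/94 |
| 70% | 70/71/88 | 85/85/93 | 91/92/95 |

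Over all scenarios run, stratifying added 0 to 7 points and the seropositive comparison was never less powerful.

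**5. Rates instead of proportions.** Section 8.3 compares rates per person-time. A Wald test on Poisson counts (control rate 0.223 per child, 50% seropositive, RR 2, halving) gives 62% for all children and 82% for seropositives, the same direction.

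**The case against.** **The whole-arm comparison is the correct estimand.** The objective concerns a strategy of screening and treating. Its effect must include seronegatives, among them carriers the test misses. This stands in full. A reader might infer that the primary analysis is biased or understates the truth. It does not: its smaller effect is the strategy effect. The seropositive comparison answers a different question, namely benefit given a positive test.

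**Ignoring serostatus barely weakens the primary test.** This also stands. The crude and stratified columns differ by about one point in the base case and by at most 7 in any scenario. The larger gains come only from changing the population.

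**The stated power is not refuted.** A reader might infer a shortfall against the figure above 90%. The documents do not support that. The figure is for the arm-level difference, comes from a transmission model that may already include seronegatives, and rests on an effect size not visible here. If it is right, the gain in seropositives is under 10 points. At 70% seropositivity in the base case it is about 4. The 30% case puts every school at the eligibility floor and lowers control risk to 16%.

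**Subgroups and covariates may sit in an SAP that is not at hand.** They may. But section 8.3 names its tests, estimates and denominators in detail and, for the efficacy comparisons, describes only whole-arm ones. A subset chosen after results are known would carry little weight.

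**A seropositive subset omits part of the intervention.** True. SSAT also treats asymptomatic slide-positive seronegatives. This is why the seronegative stratum should be shown too. Within seropositives, treatment triggered by serology and treatment triggered by the slide still overlap.

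**Conclusion.** The point holds as a gap in interpretation, not as an error in the primary analysis. Serostatus is known before treatment in every randomised child, so SSAT against control within baseline seropositives is a randomised comparison the trial can make with data it already collects. The protocol plans no such comparison.

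With 340 per arm and the assumed risks, its power is about 73%, 92% and 98% at 30%, 50% and 70% seropositivity, against 40%, 76% and 94% for all children. The difference is about 33, 16 and 4 points. The 30% and 10% risks, the halving, and the absence of effect in seronegatives are assumptions; none is in the documents. The 30-70% range is a school-level rule judged on 20 children per school, so the enrolled share may differ.

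Two further readings are not supported. A reader might treat baseline qPCR and school as strong predictors that must enter the model, or conclude that randomisation must be stratified by school. The protocol gives no figures for either as a predictor in this population. Its Background says that a single qPCR in other cohorts found only 25-30% of those who later recurred.

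**What to change.** In section 8.3, or in the SAP before any comparison by arm:

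1. Keep all randomised children as the primary population. Estimate the rate ratio stratified by, or adjusted for, baseline Luminex serostatus. Expect only a small gain in precision.
2. Pre-specify as a key secondary analysis the same SSAT against control rate ratio in children seropositive at baseline, analysed as randomised and using the same serological cut-off in both arms. Report the seronegative stratum beside it with its own interval.
3. State that this secondary analysis estimates benefit given a positive test and does not replace the strategy effect.
4. In section 8.2, state the effect size, the seroprevalence and the share of infections in seropositives behind the power figure, so that readers can see whether dilution was allowed for.

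The cost is a few sentences and one extra labelled secondary analysis. No new samples, visits or participants are needed.
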